5.1.3 Concomitant medication date imputation

The following algorithm will be used to estimate medication start dates for which only partial information is known. Note that “index date” refers to the date of Visit 1 (Screening).

Missing day and month:

- If the year is the same as the year of the index date, then the day and month of the index date will be assigned to the missing fields.
- If the year is prior to the year of the index date, then December 31 will be assigned to the missing fields.
- If the year is after the year of the index date, then January 1 will be assigned to the missing fields.

Missing month only:

- Treat day as missing and replace both month and day according to the above procedure.

Missing day only:

- If the month and year are the same as the year and month of the index date, then the index date will be assigned to the missing day.
- If the month and year are before the year and month of the index date, then the last day of the month will be assigned to the missing day.

- If the month and year are after the year and month of the index date, then the first day of the month will be assigned to the missing day.

If the imputed start date result is after the stop date (and the stop date is complete), the imputed start date will be reset to the stop date.

The following algorithm will be used to estimate medication stop dates for which only partial information is known.

Missing year:

- Date left missing.

Missing month:

- Impute ‘December’.

Missing day:

- Impute ‘last date of that month’.

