5. Completed a full course (two doses) of a COVID-19 mRNA vaccine at least  $\geq 4$  weeks after start of commercially prescribed ofatumumab for the treatment of RMS
6. Currently on commercially prescribed ofatumumab for  $\geq 4$  weeks for the treatment of RMS
7. Received two dose mRNA COVID-19 vaccine (Pfizer or Moderna vaccine)  $\geq 2$  weeks ago
8. Pre-ofatumumab serologies with Hepatitis B testing not indicative of active or latent infection
9. Total serum immunoglobulin IgG  $\geq 400$  mg/dl at Screening

Patients eligible for inclusion in Cohort 5 of this study must meet **all** of the following criteria:

1. Signed informed consent must be obtained prior to participation in the study
2. Age 18-55 years old at Screening
3. Diagnosis of relapsing MS by 2017 revised McDonald criteria
4. Must be willing to comply with the study schedule
5. Currently on commercially prescribed interferon or glatiramer acetate for  $\geq 4$  weeks for the treatment of RMS
6. Completed a full course (two doses) of a COVID-19 mRNA vaccine after start of glatiramer acetate or interferon
7. Received two dose mRNA COVID-19 vaccine (Pfizer or Moderna vaccine)  $\geq 2$  weeks ago
8. If the patient has received the mRNA booster, then the mRNA booster should be  $\geq 2$  weeks prior to enrollment.
9. Total serum immunoglobulin IgG  $\geq 400$  mg/dl at Screening

Patients eligible for inclusion in Cohort 6 of this study must meet **all** of the following criteria:

1. Signed informed consent must be obtained prior to participation in the study
2. Age 18-55 years old at Screening
3. Diagnosis of relapsing MS by 2017 revised McDonald criteria
4. Must be willing to comply with the study schedule
5. Currently on commercially prescribed ofatumumab for  $\geq 4$  weeks for the treatment of RMS

6. Completed a full course (two doses) of a COVID-19 mRNA vaccine at least  $\geq$  4 weeks after start of commercially prescribed ofatumumab for the treatment of RMS
7. Received two dose mRNA COVID-19 vaccine (Pfizer or Moderna vaccine)  $\geq$  2 weeks ago
8. Pre-ofatumumab serologies with Hepatitis B testing not indicative of active or latent infection
9. Total serum immunoglobulin IgG  $\geq$  400 mg/dl at Screening
10. Has received an mRNA booster  $\geq$  2 weeks prior to enrollment

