2.4 Treatments (study treatment, rescue medication, concomitant therapies, compliance)

2.4.1 Study treatment / compliance

Participants in all cohorts must intend to receive or have received both doses of a COVID-19 mRNA vaccine.

The following variables will be summarized descriptively as continuous variables by cohort group unless otherwise specified:

- Time (days) from first dose of ofatumumab to last dose of ofatumumab for Cohort 1 participants
- Time (days) from first dose of earliest MS DMT to:
 - first dose of COVID-19 vaccine
 - primary analysis time point (see [Section 1.1](#))
- Time (days) from first dose of most recent MS DMT to:
 - first dose of COVID-19 vaccine
 - primary analysis time point (see [Section 1.1](#))

MS treatment compliance will be listed by individual cohort and participant.

Study duration

Study duration in days will be calculated as [(date of last contact/EOS – date of Visit 1) + 1] and summarized descriptively as a continuous variable by cohort group.

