5.1.3.1 Prior therapies date imputation

Same as for medications above.

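### Partial MS-drug start dates are imputed as late as possible with no cap at the vaccine date, so a year-only start in Cohorts 4–6 can land after the vaccination it must precede

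*SAP*

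**What the plan says.** SAP 5.1.3 gives one algorithm for partial medication start dates, anchored on Visit 1.

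- Day and month missing, Visit 1 year: "If the year is the same as the year of the index date, then the day and month of the index date will be assigned".
- Day and month missing, earlier year: "If the year is prior to the year of the index date, then December 31 will be assigned to the missing fields".
- Day only missing, earlier month: "If the month and year are before the year and month of the index date, then the last day of the month will be assigned".
- The only limit on the result is a complete stop date: "If the imputed start date result is after the stop date (and the stop date is complete), the imputed start date will be reset".

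For prior therapies, SAP 5.1.3.1 reads "Same as for medications above". SAP 2.4.2 treats prior MS DMTs within the medication section and sorts medications into prior and concomitant on recorded or imputed dates.

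SAP 2.4.1 lists "Time (days) from first dose of earliest MS DMT to" the first vaccine dose and the primary analysis time point, and the same two intervals for the most recent MS DMT. It does not mention imputed dates. SAP 5.1.1 says there are no imputation rules for study drug, but the SAP does not define that term.

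Protocol 5.1 fixes the order of events. Cohorts 4 and 6 completed the two-dose course at least 4 "weeks after start of commercially prescribed ofatumumab for the treatment of RMS". Cohort 5 completed it after starting interferon or glatiramer acetate. All three cohorts had the course at least 2 weeks before entry.

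**The concern.** Moving a start date as late as possible is a usual convention for deciding whether a medication is prior or concomitant. It suits an exposure interval badly. In Cohorts 4–6 vaccination lies between drug start and Visit 1, so pushing the start towards Visit 1 can carry it past the vaccine. The derived interval then says that the participant was vaccinated before starting the drug. Yet the analysis set (SAP 2.2) holds only participants who met all entry criteria.

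The timing of vaccination relative to drug start is what separates the cohorts. The 2.4.1 intervals are the SAP's summary of drug exposure before vaccination. In groups of about 22, a few impossible values set the minimum and move the mean.

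**Working it through.** No sample size, margin of error or other stated figure depends on this rule, so there is nothing in the plan to reproduce. The check applies the algorithm to dates that satisfy the entry criteria.

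**Inputs**
- Imputation branches: SAP 5.1.3 and 5.1.3.1.
- Order of drug, vaccine and entry: Protocol 5.1.
- Spacing of doses 1 and 2: 21 days for Pfizer (Day 1 to Day 22) and 28 days for Moderna (Day 1 to Day 29), from Protocol Tables 8-1 and 8-2. Assumed to hold for Cohorts 4–6.
- Primary time point for Cohorts 4–6: Visit 2 (SAP 1.1), about 7 days after Visit 1.
- Ofatumumab approval in MS: August 2020 (Protocol 1.1).
- Calendar dates below are illustrations.

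**Formula:** interval = date of first vaccine dose − imputed DMT start date.

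**1. Day and month missing, start in the Visit 1 year.** The start becomes the Visit 1 date. If the 2 weeks are counted to Visit 1, the first dose was at least 21 + 14 = 35 days (Pfizer) or 28 + 14 = 42 days (Moderna) earlier. The interval is therefore at most −35 or −42 days. Counted to Visit 2 instead, the bounds are −35 + 7 = −28 and −42 + 7 = −35. It is negative in every case.

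**2. Day and month missing, start and first dose in the same earlier year.** The start becomes 31 December of that year. The interval is negative unless the first dose was given on 31 December itself, when it is 0.

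**3. Day and month missing, start in an earlier year, first dose in a later year.** The imputed start precedes the dose, so the interval is positive but short by 0 to 364 days. For a commercial ofatumumab start in 2020 the shortfall is at most about 152 days (1 August to 31 December).

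**4. Day only missing.** The start goes to month end, so the interval is short by 0 to 30 days, about 15 on average if starts are spread evenly.

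| Known part | True start | Dose 1 | Visit 1 | Imputed start | True days | Imputed days |
|---|---|---|---|---|---|---|
| Year | 15 Jan 2021 | 1 Apr 2021 | 15 Nov 2021 | 15 Nov 2021 | 76 | −228 |
| Year | 15 Jan 2021 | 1 Apr 2021 | 15 Feb 2022 | 31 Dec 2021 | 76 | −274 |
| Year | 1 Sep 2020 | 1 Apr 2021 | 15 Nov 2021 | 31 Dec 2020 | 212 | 91 |
| Year | 15 Jan 2021 | 20 Jan 2022 | 1 Jun 2022 | 31 Dec 2021 | 370 | 20 |
| Year (interferon) | 15 Jan 2012 | 1 Apr 2021 | 15 Nov 2021 | 31 Dec 2012 | 3364 | 3013 |
| Month | 15 Jan 2021 | 1 Apr 2021 | 15 Nov 2021 | 31 Jan 2021 | 76 | 60 |
| Month (edge) | 1 Jul 2021 | 29 Jul 2021 | 2 Sep 2021 | 31 Jul 2021 | 28 | −2 |

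In the first row, time to the primary time point falls from 311 to 7 days. In the interferon row the loss is 351/3364, about 10%. If the 4 weeks are counted to completion of the course, the edge case can reach about −23 days (Pfizer) or −30 (Moderna).

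**5. Effect on a group.** One participant at −228 instead of 76 shifts the mean of 22 by 304/22 = 13.8 days and probably sets the minimum. The median and quartiles, also reported under SAP 2.1, move much less.

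**6. Prior-DMT table.** SAP 2.4.2 defines prior as taken before the date of Visit 1. An ongoing DMT whose start is imputed to Visit 1 is no longer prior and leaves that summary. A start imputed to 31 December of an earlier year stays in.

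**The case against.** The strongest reply is that the rule may never reach these intervals. SAP 2.4.1 does not cite 5.1.3, and the only stated use of imputed dates is the prior/concomitant split. SAP 5.1.1 rules out imputation for study drug. Protocol Tables 6-1 and 6-3 list ofatumumab and interferon or glatiramer acetate as investigational or control drugs, and the glossary counts controls and background therapy as study treatment. On that reading the cohort-defining drugs are exempt.

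This stands as a real ambiguity but does not settle the matter. SAP 2.1.1 calls the same drugs additional treatment, and the earliest MS DMT may be a previous therapy that no reading of study drug covers. If the cohort drugs are exempt, their partial dates have no stated handling. A sentence is needed either way.

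It is also fair that year-only starts may be rare. A site needs a better date to show that the 4-week criterion was met, Protocol 11.2 plans queries for missing values, and Protocol 11.3 requires full verification of entry criteria. The documents do not say how many starts are partial. Queries do not always recover a date, though, and the SAP's rule governs what remains.

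A reader might infer that every partial start goes badly wrong, or that the immune response results are compromised. The documents support neither. Month-only starts err by at most 30 days. 31 December does not reverse the order when vaccination came in a later year. For long-standing interferon or glatiramer acetate the relative error is small.

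**Conclusion.** The point holds as a defect in a descriptive derivation. Applied to MS DMTs, the rule gives an impossible drug–vaccine order in Cohorts 4–6 when day and month are missing: always if the start is in the Visit 1 year, and nearly always if start and first dose share an earlier year. With vaccination in a later year the interval is short by up to about a year.

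This rests on two assumptions: that imputed dates enter the 2.4.1 intervals, which is implied but not stated, and, for the −35 and −42 day bounds, that the protocol's dose spacing applied to Cohorts 4–6. Neither the responder endpoint, its exact confidence interval nor membership of the analysis set uses these dates, and no hypothesis is tested. The practical size depends on the unknown number of year-only starts.

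**What to change.** In the SAP, exempt MS DMT start dates from the 5.1.3 rule for the 2.4.1 intervals and the prior-DMT table, and state instead:

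- Query the site first.
- If the date stays partial, either leave the interval missing or impute within the known month or year (for example the midpoint), with the imputed start not allowed after the first vaccine dose in Cohorts 2–6.
- Apply the cap to imputed dates only, so that recorded timing deviations stay visible.
- Footnote the number of imputed starts in each cohort group.
- Say whether study drug in 5.1.1 covers the commercially prescribed DMTs.

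The cost is a short SAP paragraph and one derivation change. The drawback is that capped values assume the eligibility order was met. That is why the count should be shown and why leaving the interval missing is an acceptable alternative.

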2.4.2 Prior, concomitant and post therapies

Medications will be coded using the World Health Organization (WHO) Drug Dictionary. The WHO Drug Dictionary version used for reporting the study will be indicated in a footnote on relevant outputs.

Medications will be classified as prior or concomitant as follows:

- Prior medications are defined as medications taken prior to the date of Visit 1 (Screening).
- Concomitant medications are defined as medications taken on or after the date of Visit 1 (Screening).

Medications will be categorized into the above classes based on recorded or imputed start and end dates (see [Section 5.1.3](#)).

Prior and concomitant medications will be summarized with frequency counts and percentages by cohort group, Anatomical Therapeutic Chemical (ATC) class and PT. Tables will show the overall number and percentage of participants receiving at least one medication of a particular ATC class and at least one medication of a particular PT. A separate summary of prior MS DMTs by PT will be provided.

Non-drug therapies/procedures will be coded using MedDRA terminology. The MedDRA version used for reporting the study will be indicated in a footnote on relevant outputs. Non-drug therapies/procedures will be classified as prior or concomitant based on recorded or imputed start and end dates as outlined above for medications.

Prior and concomitant non-drug therapies/procedures will be summarized by cohort group, primary SOC and PT. Tables will show the overall number and percentage of participants with at least one non-drug therapy/procedure of a particular primary SOC and at least one non-drug therapy/procedure of a particular PT.

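### SAP 5.1.3 can impute a medication start after its stop when the start is year-only in the Visit 1 year and the stop is an earlier month of that year; its prior/concomitant class then depends on an unstated programming rule

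*SAP*

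**What the plan says.** SAP 5.1.3 takes Visit 1 (Screening) as the index date. Its rules for partial start dates include:

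- Day and month missing, year of Visit 1: "If the year is the same as the year of the index date, then the day and month of the index date will be assigned".
- Day and month missing, earlier year: "If the year is prior to the year of the index date, then December 31 will be assigned to the missing fields".
- Day missing, month before the Visit 1 month: "If the month and year are before the year and month of the index date, then the last day of the month will be assigned".

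The order check comes next, with a condition attached: "If the imputed start date result is after the stop date (and the stop date is complete"). When that condition is met, the start is moved back to the stop. Only after that does the section turn to partial stops: "The following algorithm will be used to estimate medication stop dates for which only partial information is known". A missing stop month becomes December, a missing stop day becomes the last day of the month, and a stop with no year stays missing. No later step compares start with stop.

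SAP 5.1.3.1 carries the same rules to prior therapies ("Same as for medications above"), and 5.1.3.2 does so for post therapies.

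SAP 2.4.2 defines prior medications as those taken before the Visit 1 date and concomitant ones as those taken on or after it. It adds: "Medications will be categorized into the above classes based on recorded or imputed start and end dates". It does not say which of the two dates decides which class.

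**The concern.** The check exists to prevent a start later than a stop, but it is switched off when the recorded stop is itself partial. In that case a recorded fact (the stop month) is contradicted by an imputed one (the start set to Visit 1). Where the recorded stop month lies wholly before Visit 1, the drug is known to be prior only. The imputed start can nevertheless remove it from the prior tables or move it to the concomitant table. What is at stake is the accuracy of the prior and concomitant medication summaries and the separate prior MS DMT summary, plus records whose start follows their stop.

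**Working it through.** The plan states no figure that depends on this rule, so there is none to reproduce. The check applies the rule as written.

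**Worked example** (dates assumed): Visit 1 = 15-Nov-2021, recorded start 2021, recorded stop Jun-2021.

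- Imputed start: year equals the Visit 1 year, so 15-Nov-2021.
- Imputed stop: day missing, so 30-Jun-2021.
- Order check: the recorded stop is not complete, so there is no reset.
- Gap: 31 (Jul) + 31 (Aug) + 30 (Sep) + 31 (Oct) + 15 (Nov) = 138 days, start after stop.

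**Class under SAP 2.4.2.** Three programmable readings, applied to the example:

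| Reading | Prior? | Concomitant? | Result |
|---|---|---|---|
| A: prior if start < Visit 1; concomitant if stop ≥ Visit 1 | 15-Nov < 15-Nov: no | 30-Jun ≥ 15-Nov: no | neither |
| B: as A, but a start ≥ Visit 1 also makes it concomitant | no | 15-Nov ≥ 15-Nov: yes | concomitant |
| C: prior if either date < Visit 1; concomitant if stop ≥ Visit 1 | 30-Jun < 15-Nov: yes | no | prior only (correct) |

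**Which patterns fail.** The start and stop rules were applied literally to every ordered pair of true dates on a 3-day grid over 2021–2023, with an assumed Visit 1 of 15-Jun-2022. That is 365 dates, so 365 × 366 / 2 = 66,795 pairs per pattern. The counts show which patterns can fail; they are not expected frequencies.

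| Recorded start | Recorded stop | Start after stop |
|---|---|---|
| year only | month and year | 7,603 (1,275 starting in the Visit 1 year + 6,328 in an earlier year) |
| month and year | month and year | 0 |
| year only | year only | 0 |
| month and year | year only | 0 |
| year only | day and year, no month | 7,339 (all earlier year) |
| month and year | day and year, no month | 55 (all earlier year) |

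The zeros follow from the rules. A year-only stop goes to 31 December, which no imputed start in that year can pass. When both dates lack only the day, the start never falls later than the end of its own month.

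**Which inversions change class.** All 1,275 records in the Visit 1 year are truly prior only. Every one is misclassified under A (neither) and B (concomitant), and none under C. Inversions from earlier years change no class under any reading, because both imputed dates precede Visit 1. For example, start 2021 and stop Mar-2021 give 31-Dec-2021 and 31-Mar-2021, in the wrong order but both before 15-Jun-2022.

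**After the fix.** Setting the start to the earlier of imputed start and imputed stop leaves 0 inversions in every pattern and 0 misclassifications among these records under A and B. The worked example becomes 30-Jun-2021 for both dates: prior only under A, B and C.

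**The case against.** The strongest reply is that SAP 2.4.2 names both dates and defines prior as taken before Visit 1. A stop of 30-Jun-2021 shows on its own that the drug was taken before 15-Nov-2021, so a sensible programmer would reach reading C. That stands as far as it goes: misclassification is possible, not certain. But the SAP does not state reading C, and even under C the start remains later than the stop.

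It could also be said that a complete stop date means complete after imputation. The condition comes before the stop-date algorithm, and on that reading it would exclude only stops with no year. A stop recorded in full is the natural meaning.

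The pattern may be rare. Protocol 5.2 makes sites place recent steroid, S1P and natalizumab use relative to screening or enrollment, and Protocol 11.2 provides for queries on missing values. Both should reduce the number of such records; neither corrects the rule.

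A reader might infer more than the documents support:

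- *Any drug with two partial dates is affected.* It is not; most partial patterns never invert.
- *Historical treatments in general are at risk.* Drugs started in a year before Visit 1 keep their class.
- *Ended drugs would be counted as prohibited co-medication.* Protocol Table 6-2 governs actual use during the trial. The SAP does not identify prohibited use from imputed dates, and deviations are summarized separately (SAP 2.3.1).
- *Each such entry moves a percentage by 1/22 = 4.5 points in a group of 22.* SAP 2.4.2 counts participants with at least one record, so a count changes only if no other record puts that participant in the row.
- *The matching sentence in SAP 5.1.2 has the same fault for adverse events.* Adverse events begin after consent, and conditions already present go to medical history (Protocol 10.1.1). A stop month before Visit 1 should not arise.

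**Conclusion.** SAP 5.1.3 is wrong as written for a narrow set of records: taken literally, it can produce an impossible date order that nothing else in the plan corrects. Misclassification needs a year-only start in the Visit 1 year, a month-and-year stop before the Visit 1 month, and a program that decides prior status from the start date. Other inversions leave the class intact.

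The consequence is minor. It is confined to the descriptive prior/concomitant medication and prior MS DMT summaries and to inverted dates in derived data. Where a participant's only qualifying record is affected, that participant's count in the row changes. The frequency cannot be judged from the documents. Immune response and immune conversion do not use this classification. SAP 2.4.1 also has time variables counted from a first DMT dose, but the SAP does not say whether they use imputed starts, and no claim is made about them here.

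The conclusion rests on reading a complete stop date as one recorded in full. The Visit 1 dates are assumed for illustration.

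**What to change.** In SAP 5.1.3, which also serves 5.1.3.1 and 5.1.3.2: impute the stop date first, delete the parenthetical condition that the stop be complete, and set any imputed start later than the recorded or imputed stop to that stop date. In SAP 2.4.2, add that a medication whose recorded stop month or year lies wholly before Visit 1 is classed as prior only. SAP 5.1.2 needs no change on this account.

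The cost is one reworded clause, one added sentence and a small programming change. No data collection is needed.
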